8.5.2 Effect modification analyses of the primary outcome

We will examine whether pre-specified baseline variables modified the effect of treatment group on the primary outcome using tests of statistical interaction in a proportional odds regression model. Independent variables will include study group assignment, the potential effect modifier of interest, the interaction between the two, and the same pre-specified covariates used in the primary model. Presence of effect modification will be assessed by reference to the LR for the interaction term, with values greater than 6 considered to suggest a potential interaction and values greater than 7 considered to confirm an interaction.

We will examine whether the following pre-specified baseline variables modify the effect of study group on the primary outcome:

- Baseline recipient (trial participant) antibody quantification
- Baseline COVID scale
- Baseline SOFA
- ICU/ward enrollment location
- Age
- Race/ethnicity
- Duration of symptoms prior to randomization
- Mechanical ventilation status at baseline

8.6 Analysis plan for secondary endpoints

The analyses for secondary endpoints will be intent-to-treat, meaning that patients will be analyzed according to the randomization schedule regardless of the treatment administered. The following is a table of secondary endpoints and analyses (Table 2).

Table 2. Trial secondary outcomes		
Outcome	Type	Analysis
All-location, all-cause 14-day mortality (assessed on Study Day 15)	Binary	Logistic regression
All-location, all-cause 28-day mortality (assessed on Study Day 29)	Binary	Logistic regression
Survival through 28 days	Time-to-event	Proportional hazards regression
Time to hospital discharge through 28 days	Time-to-event	Multistate model with death as a competing risk
Time to recovery (defined as time from randomization to the earlier of final oxygen receipt in the hospital or hospital discharge)	Time-to-event	CPM with logit link
COVID-19 7-point Ordinal Clinical Progression Outcomes Scale on Study Day 3, 8 and 29	Ordinal	CPM with logit link
Oxygen-free days through Day 28	Ordinal	CPM with logit link
Ventilator-free days through Day 28	Ordinal	CPM with logit link
Vasopressor-free days through Day 28	Ordinal	CPM with logit link
ICU-free days through Day 28	Ordinal	CPM with logit link
Hospital-free days through Day 28	Ordinal	CPM with logit link

8.6.1 Ordinal outcomes

Ordinal secondary outcomes will be analyzed using the same model described for the primary endpoint. Similar steps to evaluate model fit and overly influential observations will be performed.

8.6.2 Binary outcomes

Binary secondary outcomes will be analyzed using multivariable logistic regression models with the same pre-specified covariates as the primary endpoint. To assess model calibration and overly influential observations, graphical displays of calibration and DFBETAS will be created.

8.6.3 Time to event outcomes

Survival will be analyzed with a proportional hazards regression model. The key result of the analysis is an estimate of the treatment effect hazards ratio. The same set of covariates used for the adjusted analysis of the primary endpoint will also be included in the analysis of secondary time-to-event endpoints. Model fit will be assessed with Schoenfeld residuals and with leave-one-out diagnostics like DFBETAS. The proportional odds assumption will be evaluated with graphical displays. Deviations from proportionality will trigger sensitivity analyses.

8.6.4 Outcomes with a competing risk of death

Some secondary outcomes, like the primary outcome, incorporate death as part of the scale. Others, such as time to discharge, do not. Because death censors length of stay, it is a competing outcome. Outcomes with a competing risk of death will be analyzed with a multi-state model. Both the instantaneous risk and cumulative risk of the outcome will be reported.

8.6.5 Missing data

If missing covariate data occurs, then multiple imputation methods similar to those described for the primary endpoint will be used to estimate the point estimate and confidence interval for the secondary endpoints.

8.7 Safety Outcomes and Adverse Events

The frequency and description of safety outcomes and adverse events will be reported. The association between intervention group and safety outcomes will be estimated without covariate adjustment. The following table lists the safety outcomes and the planned analyses (Table 3).

Table 3. Trial safety outcomes.		
Outcome	Type	Analysis
Receipt of renal replacement therapy	Binary	Risk difference
Documented venous thromboembolic disease (DVT or PE)	Binary	Risk difference
Documented cardiovascular event (myocardial infarction or ischemic stroke)	Binary	Risk difference
Transfusion reaction (fever/rash)	Binary	Risk difference
Transfusion related acute lung injury (TRALI)	Binary	Risk difference
Transfusion associated circulatory overload (TACO)	Binary	Risk difference
Transfusion related infection	Binary	Risk difference

9. DATA QUALITY MONITORING AND STORAGE

9.1 Data Quality Monitoring

Data quality will be reviewed remotely using front-end range and logic checks at the time of data entry and back-end monitoring of data using application programming interface tools connecting the online database to statistical software to generate data reports. Patient records and case report forms will also be reviewed by the Vanderbilt Coordinating Center (VCC) to evaluate the accuracy and completeness of the data entered into the database and monitor for protocol compliance per the study monitoring plan. The VCC will perform remote monitoring of each study site to examine the completeness and accuracy of informed consent documents for study participants, documentation of eligibility criteria, and the completeness of study outcome collection. Fully identifiable source documents will be requested from participating sites in order to carry out the study monitoring plan.

9.2 Data Storage

Data will be entered into a secure online database. All data will be maintained in the secure online database until the time of study publication. At the time of publication, a de-identified version of the database will be generated.

10. RISK ASSESSMENT

10.1 Potential Risk to Participants

Although convalescent plasma is an FDA approved treatment with an established safety profile, potential risks exist to participating in this study of convalescent plasma versus placebo for the treatment of COVID-19.

10.1.1 Potential risks of receiving convalescent plasma

One potential risk to receiving convalescent plasma is the possibility of developing antibody-mediated enhancement of infection (ADE). ADE can happen in the setting of viral and bacterial diseases and occurs when antibodies increase the severity of disease. ADE has been described in other types of coronaviruses, and it is also possible that antibodies to one type of coronavirus could enhance disease with another strain.⁴³ However, in the setting of MERS and the closely related SARS-CoV-1, evidence suggests that the use of convalescent plasma is safe.^{7,28,44} Anecdotal evidence of the use of convalescent plasma in COVID-19 also indicates that this is a safe treatment option.^{32,33} Another possible risk to receiving convalescent plasma is that the patient may mount a sub-optimal humoral immune response resulting in susceptibility to reinfection as has been seen with respiratory syncytial virus.⁴⁵ However, these concerns seem minor as compared to the possibility of limiting the duration and severity of disease, and avoiding interventions like mechanical ventilation, ARDS and sepsis. There are also risks associated with any transfusion of plasma including transmission of transfusion transmitted viruses (e.g. HIV, HBV, HCV, etc.), allergic transfusion reactions, anaphylaxis to transfusion, febrile transfusion reaction, transfusion related acute lung injury (TRALI), transfusion associated cardiac overload (TACO), and hemolysis should ABO incompatible plasma be administered. Another risk of plasma is thrombotic (clotting) complications, such as deep venous thrombosis, pulmonary embolism, myocardial infarction, and stroke. All study participants will be closely monitored for adverse events by study personnel.

10.1.2 Potential risks of receiving lactated Ringer's solution with multivitamins with COVID-19

One potential risk to participating in this study is receiving LR with multivitamins rather than convalescent plasma. This risk is only relevant if convalescent plasma is ultimately found to be an effective therapy for COVID-19 and is not relevant if convalescent plasma is ultimately found to be an ineffective therapy for COVID-19. This trial protocol minimizes this risk through rigorous design to minimize the number of patients who must be enrolled to determine whether convalescent plasma is an effective therapy for COVID-19. The other risks of receiving LR are very low and include volume overload and allergic reaction to multivitamins. All study participants will be closely monitored for adverse events by study personnel.

10.2 Minimization of Risk

Federal regulations at 45 CFR 46.111(a)(1) require that risks to participants are minimized by using procedures which are consistent with sound research design. This trial protocol incorporates numerous design elements to minimize risk to patients that meet this human subject protection requirement. Convalescent plasma has been approved by the Food and Drug Administration and has been used in clinical practice for decades in a number of patient populations with an established safety profile. The dose and route of administration of convalescent serum in this trial are comparable to the dose and route of administration approved for the treatment of other acute viral infections such as SARS and MERS. The trial protocol includes monitoring of adverse events, clinical outcomes, and interim analyses by an independent data and safety monitoring board empowered to stop or modify the trial at any time. In addition, all patients will be hospitalized or in an ED with plans to be hospitalized. They will be closely monitored by nursing staff during the infusion of the plasma.

10.3 Potential Benefit

Study participants may or may not receive any direct benefits from their participation in this study. Administration of convalescent plasma may improve clinical outcomes among adults hospitalized for COVID-19 infection.

10.4 Risk in Relation to Anticipated Benefit

Federal regulations at 45 CFR 46.111 (a)(2) require that "the risks to subjects are reasonable in relation to anticipated benefits, if any, to subjects, and the importance of the knowledge that may reasonably be expected to result." Based on the preceding assessment of risks and potential benefits, the risks to subjects are reasonable in relation to anticipated benefits. Convalescent plasma has been used in clinical practice for decades and previously evaluated for the treatment of patients acutely ill from infection with substantial data to support its safety and potential efficacy.

11. HUMAN SUBJECTS PROTECTIONS

Each study participant will undergo a consent process as outlined above. Approval of the central institutional review board will be required before any participant is entered into the study.

11.1 Selection of Subjects

Federal regulations at 45 CFR 46(a)(3) require the equitable selection of subjects. The emergency departments, hospital wards, and ICUs of participating sites will be screened to determine if any patient meets inclusion and exclusion criteria. Data that have been collected as part of the routine clinical care of the patient will be reviewed to determine eligibility. If any patient meets criteria for study enrollment, then the attending physician responsible for his or her care will be asked for permission to approach the patient or his or her LAR for informed consent. Study exclusion criteria neither unjustly exclude classes of individuals from participation in the research nor unjustly include classes of individuals for participation in the research. Hence, the recruitment of participants conforms to the principle of distributive justice.

11.2 Justification of Including Vulnerable Subjects

The present research aims to investigate the safety and efficacy of convalescent plasma for the treatment of patients with COVID-19 who are at high risk for respiratory failure and mortality. Due to the nature of this patient population, many of these patients will have impaired decision-making capabilities. Moreover, those with intact decision-making capacities probably have milder disease than those with impaired capacity. Therefore, the validity of the study and its generalizability to severely ill patients would be compromised by enrolling only those participants with retained decision-making capacity. Hence, participants recruited for this trial are not being unfairly burdened with involvement in this research.

11.3 Informed Consent

Federal regulations 45 CFR 46.111(a)(5) require that informed consent will be sought from each patient or the patient's LAR. Study personnel obtaining informed consent are responsible for ensuring that the patient or LAR understands the risks and benefits of participating in the study, answering any questions the patient or LAR may have throughout the study and sharing any new information in a timely manner that may be relevant to the patient's or LAR's willingness to permit the patient's continued participation in the trial. The study personnel obtaining informed consent will make every effort to minimize coercion. All patients or their LARs will be informed of the objectives of the study and the potential risks. The informed consent document will be used to explain the risks and benefits of study participation to the patient or LAR in simple terms before the patient is entered into the study, and to confirm that the patient or LAR is satisfied with his or her understanding of the risks and benefits of participating in the study and desires to participate in the study. The investigator is responsible for ensuring that informed consent is given by each patient or LAR. This includes obtaining the appropriate signatures and dates on the informed consent document prior to the performance of any protocol procedures including administration of study agent.

For additional details, see Section 4.

11.4 Continuing Consent

Patients for whom consent was initially obtained from a LAR, but who subsequently regain decision-making capacity while in hospital will be approached for consent for continuing participation, including continuance of data acquisition. The consent form signed by the LAR should reflect that such consent should be obtained. The process for obtaining consent from these patients will be the same as that outlined in section 4.

11.5 Withdrawal of Consent

Participating patients may withdraw or be withdrawn (by the LAR, treating physician, or investigator) from the trial at any time without prejudice. Data recorded up to the point of withdrawal will be included in the trial analysis, unless consent to use data has also been withdrawn. Withdrawal of consent prior to randomization will constitute a screen-failure and will be recorded. Withdrawal of consent after randomization will lead to discontinuation of study interventions but site staff will request access to medical records for data related to the trial.

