4.7 Randomization and Blinding

Participants confirmed to meet all eligibility criteria who have provided informed consent will be randomized 1:1 to convalescent plasma versus placebo. A randomized group assignment will be provided from a centralized, web-based platform to an unblinded study personnel or delegate, who will order the study product (convalescent plasma or matching placebo). Randomization will require provision of the screening number and confirmation of patient eligibility.

Randomization will be completed in permuted blocks and stratified by site, sex, and age. Randomization will be accessed through Research Electronic Data Capture (REDCap). The randomization module in REDCap allows the statistician to load a randomization table that will allow the study personnel to click a 'randomize' button. REDCap is a secure, web-based application designed to support data capture for research studies, providing 1) an intuitive interface for validated data entry; 2) audit trails for tracking data manipulation and export procedures; 3) automated export procedures for seamless data downloads to common statistical packages; and 4) procedures for importing data from external sources.

Patients, families, and outcome assessors will be blinded to treatment arm assignment. All other study personnel will be encouraged to remain blinded to the participant's treatment assignment. Additional blinding procedure information will be in the PassItOn Blinding Procedure Document.

Plasma can vary in color, volume, and viscosity depending on donor variables. Therefore, developing a universal matching placebo is not possible. In this trial, the placebo solution is lactated Ringer's with multivitamin additives, which looks similar to plasma. The goal of the placebo solution is to maintain blinding of the participant, outcome assessors, and study personnel who are not closely involved in administering the study product. Clinical personnel who administer the study product (convalescent plasma vs placebo) such as the bedside nurse, will not be blinded. As an additional layer of blinding for the participant, plasma and placebo will be placed in matching blinding bags prior to administration.

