8.3.2 Missing data

We anticipate rare or no missingness for data points during a patients in-hospital course. There may be missing data for the COVID-19 7-point Ordinal Clinical Progression Outcomes Scale score after hospital discharge, which relies on phone follow-up. After discharge, distinguishing between category 1 and category 2 on the scale requires speaking to the participant or surrogate about normal daily activities. If the patient is not reached for follow-up phone calls after discharge, the COVID-19 7-point Ordinal Clinical Progression Outcomes Scale score will be classified as category 2 (not hospitalized, but unable to resume normal activities). If the patient is reached for a follow-up call post-charge and reports category 1, this classification of category 1 will be carried forward to future follow-up calls if the patient cannot be reached. For example, if the patient cannot be reached for the Day 8, 15, or 29 follow-up calls, a category 2 score will be reported for all three visits. If the patient is successfully contacted on the Day 8 call and reports category 1, and then the patient cannot be reached for a Day 15 call, the category 1 score from Day 8 will be carried forward to Day 15.

Missing data for a covariate used in the primary model will be multiply imputed using predictive mean matching if number of observations missing covariate values exceeds 5 percent. If fewer than 5% of observations have missing covariate values, missing values will be imputed with a single conditional mean.

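### Protocol 11.5 lets clinicians who need not be blinded withdraw a patient from the whole trial, and no rule secures or analyses that patient's Day 15 or Day 29 outcome

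*Protocol*

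**What the plan says.** Protocol 11.5 opens: "Participating patients may withdraw or be withdrawn (by the LAR, treating physician, or investigator) from the trial at any time without prejudice". It continues: "Data recorded up to the point of withdrawal will be included in the trial analysis, unless consent to use data has also been withdrawn". For withdrawal of consent after randomization, it says study interventions stop but "site staff will request access to medical records for data related to the trial". Clinician withdrawal has no criteria, and stopping treatment is not distinguished from ending follow-up.

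Other relevant places:

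- **Treatment.** Protocol 5.1 gives one infusion within 24 hours of randomization. Section 5.6 separately covers when the infusion is stopped.
- **Blinding.** Protocol 4.7 says "Patients, families, and outcome assessors will be blinded to treatment arm assignment". It adds "All other study personnel will be encouraged to remain blinded to the participant's treatment assignment", and also "Clinical personnel who administer the study product (convalescent plasma vs placebo) such as the bedside nurse, will not be blinded".
- **Analysis set.** The primary analysis (Protocol 8.3, SAP 3) and the secondary analyses (Protocol 8.6, SAP 6) are intent-to-treat: "patients will be analyzed according to the randomization schedule regardless of the treatment administered".
- **Missing outcomes.** Protocol 8.3.2 says "We anticipate rare or no missingness for data points during a patients in-hospital course", and SAP 3.2 agrees. The rule that follows assigns category 2, or a carried-forward category 1, to discharged patients who are not reached by phone.
- **Vital status.** Protocol 7.3.1 plans a search for patients not reached for the Day 29 visit. Withdrawn patients are not mentioned.
- **Sensitivity analysis.** SAP 3.3 plans a per-protocol analysis and nothing for withdrawn patients.

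**The concern.** Once the single infusion has run, withdrawal from the trial mainly ends follow-up. It would also end the Day 2 research blood draw and the protocol laboratory tests, but there is no further study treatment to stop. Section 11.5 still gives this power to people other than the patient or LAR. They may act at any time and for any reason, and they may know the arm.

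If withdrawal is related to how the patient is doing, the missing outcomes are informative. Patients who are worsening carry the worst Day 15 categories and the deaths. Uneven loss between the arms would bias the primary odds ratio, 14- and 28-day mortality, and the interim mortality comparison that can stop the trial. The analysis plan has no step that would limit or reveal this.

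**Working it through.** **Inputs from the documents.** 500 patients per arm; efficacy asserted at a likelihood ratio of 7; simulated type I error 0.02; 80% power at an odds ratio (OR) of 0.73 (Protocol 8.1, SAP 4); likelihood ratio threshold 3.3 at the 750-patient mortality look (Protocol 8.2).

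**Inputs assumed.** The documents give no withdrawal rate, no Day 15 distribution and no mortality. I take 5 or 10 losses in one arm, mortality of 10%, 15% or 20%, and the Day 15 distributions stated below. Nothing is recovered for the lost patients. Covariates are ignored.

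**Step 1. Reproduce the plan's figures.** With a normal likelihood, a ratio above 7 means z > √(2 ln 7) = 1.973, a one-sided tail of 0.024. That fits the stated 0.02. For power, SE(log OR) = √[12 / (N(1 − Σp̄³))]. With 1 − Σp̄³ = 0.96 and N = 1000, SE = √(12/960) = 0.1118. Then |ln 0.73| / 0.1118 − 1.973 = 2.815 − 1.973 = 0.842, which gives power 0.80. Values of 0.93 and 0.98 give 0.787 and 0.808. The stated power is reproduced for a well-spread outcome.

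**Step 2. Mortality odds ratio under no effect.** With D deaths per arm and 10 future deaths lost from plasma, OR = [(D − 10)/(500 − D)] / [D/(500 − D)] = (D − 10)/D. Loss from control gives the inverse.

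| Mortality | D | 10 lost from plasma | 10 lost from control |
|---|---|---|---|
| 10% | 50 | 40/50 = 0.80 | 50/40 = 1.25 |
| 15% | 75 | 65/75 = 0.87 | 75/65 = 1.15 |
| 20% | 100 | 90/100 = 0.90 | 100/90 = 1.11 |

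With 5 lost from plasma the values are 0.90, 0.93 and 0.95. Equal losses of this kind in both arms give no shift under the null.

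**Step 3. Day 15 scale under no effect.** I fitted a proportional odds model to an assumed distribution of 30/30/4/10/6/8/12% across categories 1 to 7 and removed plasma patients equally from categories 6 and 7.

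- 5 lost: OR 0.975, false-positive rate 0.040.
- 10 lost: OR 0.951, SE about 0.113. The shift is |ln 0.951| / 0.113 = 0.44 SE, so the tail beyond 1.973 − 0.44 = 1.53 is about 0.063.

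Three other assumed distributions, with losses taken from categories 6 and 7 in proportion, give 0.038-0.042 for 5 lost and 0.058-0.069 for 10 lost. If the 10 were coded category 2, by stretching the phone rule to them, the rate would be 0.072-0.104.

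**Step 4. The other direction.** With a true OR of 0.73 and the first distribution above, losing 10 category 6/7 patients from control moves the estimate to 0.766 and cuts power from 0.79 to 0.64.

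**Step 5. Interim mortality look at 750.** The threshold is z > √(2 ln 3.3) = 1.545. Assume true mortality of 18% on plasma and 12% on control, 375 per arm. In full, z = 0.06/0.0260 = 2.31, and the chance of stopping at that look is 0.78. With 8 plasma deaths lost, plasma mortality is 59.5/367 = 16.2%, z = 0.0421/0.0255 = 1.65, and the chance falls to 0.54. Losing control deaths would make a stop more likely.

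**The case against.** Several points on the other side stand.

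- **Data use.** A reader might infer that data are used only up to withdrawal. The text says such data will be included; it does not say that later data are barred. One can also argue that a clinician's act does not revoke the patient's consent, so record review could continue. That is a fair reading, but 11.5 does not state it, and the records request is tied to withdrawal of consent and is only a request.
- **Intent-to-treat.** A reader might infer that 11.5 contradicts the intent-to-treat plan. It does not. Nothing excludes withdrawn patients from the analysis; their outcomes are simply not provided for.
- **Motive.** A reader might suppose clinicians would withdraw patients to give open-label plasma. They need not: Protocol 5.4 discourages it and tracks it as a deviation, and 7.2 records it. Other treatment is left to the clinician. If it did happen, placebo patients would be the likelier ones, which biases against plasma.
- **Blinding.** The staff named as unblinded are those who administer the product, and bedside nurses are not among those who may withdraw a patient. The documents do not say that treating physicians are unblinded; they only fail to require blinding.
- **Recovery.** Inpatient Day 15 status comes from the health record (SAP 8), as do in-hospital deaths (SAP 10.1, 10.2), and the vital-status search may find others. Some outcomes would be recovered. No text says these routes apply after withdrawal by a clinician, and a vital-status search cannot supply categories 3 to 6 at Day 15.

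The figures are also worst cases: all losses fall in one arm, all have bad outcomes, and none are recovered.

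**Conclusion.** The point holds as an unaddressed risk of informative missing outcomes. The protocol permits withdrawal of a patient from the whole trial by clinicians who need not be blinded, without criteria, and neither document secures or analyses the later outcome of an inpatient withdrawn this way. The documents do not show that selective withdrawal will occur, and the direction of any bias is open.

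The size depends wholly on assumed losses. At 1-2% of one arm, the effect is small on the Day 15 odds ratio (about 0.98 to 0.95) but not on the error rate, which rises from 0.024 to about 0.04 and then to about 0.06-0.07. Mortality is more sensitive. That is enough to justify a change that costs little.

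**What to change.** In Protocol 11.5, separate discontinuation of study procedures from withdrawal of consent for data collection:

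1. Withdrawal by a treating physician or investigator does not end outcome collection. Chart review, the Day 8, 15 and 29 contacts and the vital-status search continue.
2. Only the patient or LAR can end follow-up. When they do, ask whether chart-based Day 15 status and vital status to Day 29 may still be collected.
3. Record who withdrew each patient and why, and report this by arm.

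In the SAP, state that all randomized patients stay in the intent-to-treat set, give the rule for a withdrawn patient without a Day 15 value, and add a worst-case sensitivity analysis for such patients. The infusion-stopping criteria in Protocol 5.6 are not affected.

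The cost is protocol, consent and SAP wording, plus a few record checks or calls using procedures the trial already has.
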